### 1 INTRODUCTION

Interstitial cystitis (IC) is an inflammatory disease of the bladder characterized by urinary urgency, frequency, and suprapubic pain. An estimated 1,000,000 persons are currently diagnosed with IC in the United States, however, the number of undiagnosed individuals affected may be much higher (1-3). Approximately ninety percent of IC sufferers are women (2;4). The mean age at diagnosis is 40 years with 25% of IC patients being younger than 30 years (5). Interstitial cystitis patients scored worse on quality of life questionnaires than patients on dialysis(5;6). Sixty percent of IC sufferers complain of pain with sexual intercourse, many so severe they abstained altogether (6;7). Fifty percent of IC patients are unable to work full time (8). On average, \$170 million per year is spent for medical care of interstitial cystitis. While combining lost wages and medical expenses, the economic impact of IC has been estimated to be \$1.7 billion per year (9). The cause of IC is unknown despite a century of study. Current treatments for IC have come largely from case reports and limited studies. The IC patient will often endure years of failed treatments before even some relief is achieved, if at all.

Symptoms form the basis for diagnosis of IC (4) since pathognomonic markers have yet to be identified. Several characteristics, while not diagnostic for IC, have appeared with relative frequency in advanced cases (10). These characteristics include the presence of glomerulations and/or petechial hemorrhages following bladder distention (11). Small urothelial fissures known as Hunner's ulcers have also been noted in severe cases (12)

 Since the etiology and pathogenesis of IC are still undetermined (13), directing treatments towards the specific cause(s) of the symptoms is problematic. Various IC treatments are used. Some are directed specifically to one of the proposed etiologies, whereas others are purely empirical (14). At this time, there is very little knowledge to help clinicians choose which treatments may be most beneficial for specific patients (15).

The number of current treatments is large and ranges from simple bladder distention to cystectomy with urinary diversion. IC treatments can be grouped into five broad categories:

1. intravesical therapies (e.g., Clorpactin (11), DMSO (16;17), heparin, oxychlorosene sodium (18)),

2. oral medications (e.g., pentosan polysulfate (19), amitriptyline (17), hydroxyzine (20)),

3. local ablative or injection therapy (e.g., transurethral resection (21)),

neural ablative therapy (e.g., cystolysis (22)), and
 other surgical procedures or alternative approaches (e.g., augmentation cystoplasty (23), electrical stimulation and biofeedback (24)).

In most cases of IC, treatment choices are made by first trying the safest and least invasive options, and then progressing to other treatments (which have more potential morbidity) if the initial treatments do not relieve symptoms effectively (14). Combining treatments is often needed to improve functional outcome (14:15).

47 Having failed conservative therapy, patients with refractory interstitial cystitis choose to 48 undergo various intravesical treatments to obtain symptom relief. Many of these 49 treatments, however, have failed to demonstrate sustained benefit (18).

50 51

52

53

54

55

Intavesical Bacillus Calmette-Guerin (BCG) is a novel therapy for the treatment of IC (25). Although this therapy has been used effectively in the treatment of bladder cancer, its exact mechanism of action is unknown (26-28). Preliminary studies evaluating its effect in the treatment of IC have shown promising results (25;29;30). Confirmation of these results require further clinical trial investigation with placebo control, and studies to evaluate mechanism of action and effect on putative IC markers (31-34).

56 57

## **2 STUDY DESIGN AND OBJECTIVES**

58 59 60

The proposed randomized clinical trial (RCT #2) will utilize a 2 arm design to evaluate the efficacy of intravesical BCG in patients with interstitial cystitis, as compared to an intravesical placebo.

62 63 64

61

The primary objectives of this trial are:

65 66

67

1. To compare treatment with six (6) instillations of BCG to sham treatment with six (6) instillations of saline for effects on symptoms and overall well being in patients with interstitial cystitis (IC).

68 69 70

2. To evaluate changes in urinary markers over time and correlate these changes with changes in symptoms over the same period.

71 72 73

3. To evaluate measures of symptoms and quality of life, including the O'Leary-Sant and Wisconsin symptom indices, and validate their use as endpoints in clinical trials.

74 75 76

4. To obtain additional information on re-induction of intravesical BCG.

77 78

5. To obtain information on long-term response of those patients determined to be responders at the completion of Phase 1 of treatment.

79 80 81

82 83

84

85

All participants who meet eligibility criteria at baseline screening (a two-to-four week period), will be stabilized on their current IC medications prior to randomization to one of the two treatment arms. Immediately after randomization, there will be a two-week window in which the first instillation must occur. The instillation regimen will require that the interval between treatments be a minimum of 6 days and a maximum of 3 weeks.

86

No more than 3 weeks may lapse between instillations. Each patient is expected to 87 receive total of six instillations (BCG or saline). Instillations will be scheduled according

88 to the patient's tolerability. The six instillations can be given weekly within 6

89 consecutive clinic visits, but all instillations, even if fewer than six, must be administered

90 within a 10 week visit schedule. For the six months following the intravesical instillations, each patient will continue to be monitored for safety, use of concomitant medications (especially narcotics and medications for IC), quality of life, IC symptoms, and urinary biomarkers.

93 94 95

96

97

98

91

92

The primary endpoint will be evaluated at the patient's visit at week 34 following randomization in the post-treatment follow-up phase. Patients will be identified as responders and non-responders at week 34 based on their response to the global assessment question and their use of medications for IC symptoms.

99 100

101 102

103

104

105106

107

108

The study consists of two phases as outlined below. The first phase, consisting of initial treatment and follow-up for primary and secondary endpoints, represents the primary phase of the study. Phase 2-Non-Responders will be primarily descriptive, and will provide additional information related to open-label BCG treatment for all "non-responders" in Phase 1 who choose to undergo a second course of treatment. Phase 2R-Responders will also be primarily descriptive. This phase will provide information on the long-term response of those patients determined to be "responders" at the completion of Phase 1 of treatment.

## Figure 1

109 110

111

112

113

# Phase 1

ICCTG
RANDOMIZED
CLINICAL TRIAL #2
Study Design Schematic

114 115 116

117

118

119

120

ESTABLISHED IC PATIENTS Recruitment and Prescreening Process Baseline
Visit #1
to assess
eligibility,
perform lab
tests

Baseline Visit #2 to enroll and randomize Treatment
Phase
Weeks 1-10
Clinic Visits
BCG or Sham
(6 instillations)

Post Treatment Follow-Up Phase 24 Weeks (6 months) Weeks 11-34

Primary End-point Week 34

121 122 123

## Phase 2 - Non-Responders - Open Label BCG Treatment

124 125

(-) Treatment Response at Week 34 Offer Open Label of BCG Treatment
Phase
Weeks 35-44
Clinic Visits
BCG Treatment
10 Weeks
(6 instillations)

Post BCG Treatment Follow-Up Phase Week 68 24 Weeks 2 ARM STUDY DESIGN
SHAM BCG

126127

## Phase 2R – Responders – Long-Term Response

128

(+) Treatment Response at Week 34 Long Term Response Follow-Up Long-Term Response Follow-Up 3 contacts (Week 46, 56 & 68) 30 Weeks

### 3 Study Agent and Rationale for Use in Interstitial Cystitis

129130

### 3.1 Bacillus Calmette-Guerin (BCG)

131 132 133

134

135

136

137

138

139

140

141

142

143

144145

146

147

Bacillus Calmette-Guerin is an attenuated strain of the bovine tuberculosis bacterium (Mycobacterium bovis), originally developed as a vaccine against Mycobacterium tuberculosis, the cause of tuberculosis in humans. BCG administered intravesically, is a Food and Drug Administration approved treatment for superficial cancer of the bladder (26;27). Although its exact mechanisms of action are unknown, intravesical instillations of BCG have been shown to be effective treatment of and prophylaxis against recurrent stages Ta and T1 bladder tumors and therapy for carcinoma in situ (35). Intravesical BCG is a novel therapy for the treatment of IC. An open-label pilot study of BCG for the treatment of refractory IC was conducted by Zeidman and coworkers on patients who had failed conservative therapy. Results suggested that BCG immunotherapy may be efficacious in the treatment of IC symptoms (25). Peters and colleagues extended the work of Zeidman in a placebo-controlled study. The results from this study demonstrated a 60% BCG response rate compared to a 27% placebo response. The treatment regimen was six weekly instillations of BCG. A follow-up study suggested that the results were durable. Patients treated with intravesical BCG achieved remission and remained free of IC related symptoms for more than two years (29;30).

148149150

151

152153

The mechanism of symptom relief is unknown. One theory is that BCG changes bladder inflammation from a predominantly T-helper cell type 2 (Th2) response to a Th1 response, which is more indolent (30). Another theory is that BCG may increase nitric oxide synthase activity in the bladder (30). The major concern with BCG is that this live organism occasionally causes sepsis when used to treat bladder cancer. To date, BCG sepsis has not occurred in the IC population (15).

155156157

158

159

160

154

Clear demonstration of the benefit of BCG immunotherapy would profoundly alter the current treatment options available for treating this enigmatic disease and provide insights into its etiology. Finally, a second induction of BCG for non-responders is a standard therapy for bladder cancer (36;37). If this proves to be fruitful in treating refractory IC, it will be of great benefit to those suffering from this disease.

### 4 Study Plan

### 4.1 Phase 1

The first phase, consisting of initial treatment and follow-up for primary and secondary endpoints, represents the primary phase of the study. This phase will utilize an intention-to-treat analysis to compare the proportion of responders between treatment arms, using a definition of response based on both patient assessment of global improvement and the use of "breakthrough" medications (see section 4.3.1) for symptoms.

### 4.2 Phase 2 and Phase 2R

Phase 2 of the study will include only patients who, after completing phase one study treatment and post-treatment follow-up, are classified as "non-responders" for the primary endpoint at week 34. These patients will be offered a second series of six (6) intravesical instillations with open-label BCG. For those patients originally randomized to saline, this will be the first BCG treatment. For those who originally received BCG, this will represent "reinduction therapy". The original treatment assignment will remain blinded, except for emergency situations, until the end of the study. Those patients who choose to undergo this second instillation will be followed using the same schedule as for Phase 1. Therefore, these patients will be followed a total of 34 weeks in the first treatment phase and 34 weeks in the second treatment phase for a total of 68 weeks.

Phase 2R of the study will include only patients who, after completing Phase 1 treatment and follow-up, are classified as "responders" for the primary endpoint at week 34. Three telephone contacts (or clinic visit contacts if the patient prefers) wherein the patient will be queried as to any (serious) adverse events, supplemented with mailing of data forms from the patient to the clinical center, will be conducted. At the primary endpoint of Phase 1 of the study (7.5 months from randomization), the principal investigator may choose to discuss with those patients who feel they are in excellent control of their symptoms the possibility of tapering medications for IC. The decision to initiate the discussion about medication taper, and any subsequent decision to taper medication or not, should be based on the principal investigator's impression of what is in the patient's best individual clinical interest, and will be completed only with qualified medical supervision.

For both Phase 2 and for Phase 2R, the overall global assessment of response, symptom index, and other endpoints (described in section 4.4) will be evaluated at week 68 and compared to both values at randomization and those at the end of Phase 1 (34 weeks). However, it is recognized that there is no control group for this second phase (phase 2 and phase 2R) of the study, and the analysis of these results will be primarily descriptive.

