# **4.4 Study Endpoints**254

## 4.4.1 Primary Endpoint

The primary endpoint on which the comparative efficacy of BCG and saline will be evaluated is a combined endpoint with two components: the patient-reported global assessment of response and the use of IC medications during the follow-up period.

The global evaluation of improvement for the primary endpoint will occur at week 34 or withdrawal, whichever comes first, relative to IC symptoms at baseline via the question: "As compared to when you started the study, how would you rate your interstitial cystitis symptoms now?" A seven point scale centered at zero will be used: -3) markedly worse; -2) moderately worse; -1) slightly worse; 0) no change; +1 slightly improved; +2) moderately improved; and +3) markedly improved. Participants who answer either +2) moderately improved or +3) markedly improved on the global evaluation will be considered to have evidence of "clinical improvement"

The second component relates to changes (increase or addition) in the use of IC treatment medications from the level at which the patient was stabilized at the beginning of the study. Increased usage of pre-study IC medications or the initiation of new IC medications during the last four weeks of post-treatment follow-up (week 31 - 34 post-randomization) will cause the patient to be classified as a non-responder.

Use of *breakthrough* medications as described in Section 4.3.1 will be allowed **with the exception of narcotic analgesics.** New or increased use of narcotic analgesics during the last four weeks of post-treatment follow-up (week 31-34) will be considered equivalent to starting a new IC medication, and therefore, would cause the patient to be classified as a non-responder. In addition, any patient who requests narcotic analgesics for treatment of IC symptoms during the last four weeks of post-treatment follow-up will also be classified as a non-responder.

Therefore, patients will be considered to be "responders" for the primary endpoint if they fulfill both of the following two criteria:

1. Report "moderate" or "marked" improvement on the global assessment at 34 weeks.

2. Report no increase in pre-study IC medications, and no initiation of new IC medications, and no new or increased use of narcotic medications during the final 4 weeks of the follow-up phase.

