### 6.2.1 Inclusion Criteria

- 1. At least 18 years of age.
- 2. Participant must sign and date the informed consent.
- 3. Participant must have received a minimum of 12 weeks of treatment with some standard form of therapy or combination of therapies for IC. The treatment must have occurred after diagnosis of IC and administered in response to the patient's IC symptoms. Potential previous therapies include: tricyclic antidepressants, hydroxyzine, other antihistamines, DMSO, pentosanpolysulfate, heparin, NSAIDS, and anticholinergies.
- 4. Participant (male or female) must agree to use a medically approved method of birth control.
- 5. Participant must report a urinary frequency of at least 11 times per 24-hour day, on average over the previous four weeks. This frequency criterion must be met at each of the two baseline-screening visits as reported by the participant.
- 6. Participant must report a pain/discomfort score of 4 or greater on a 0 9 Likert scale. This pain/discomfort criterion must be met at each of the two baseline-screening visits.
- 7. These reported urinary symptoms of frequency and pain/discomfort must have been present for at least the previous 24 weeks prior to the first baseline screening visit.
- 8. Participants must report in the baseline voiding diary at least one voided volume greater than or equal to 75cc in a 24 hour period.

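### Section 4.2 splits patients on week-34 status and then uses week 34 as one of two references for week 68, so regression to the mean alone will look like gain in Phase 2 and lost response in Phase 2R

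*Protocol*

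**What the plan says.** Section 4.2 defines the two follow-on cohorts by the same single classification. Phase 2 takes only patients who "are classified as 'non-responders' for the primary endpoint at week 34"; Phase 2R takes only those who "are classified as 'responders' for the primary endpoint at week 34". For both cohorts the global assessment, symptom index and other endpoints "will be evaluated at week 68 and compared to both values at randomization and those at the end of Phase 1 (34 weeks".

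The classification comes from section 4.4.1. One of its two criteria is the rating at one visit: "Report 'moderate' or 'marked' improvement on the global assessment at 34 weeks". The other is medication use in weeks 31 to 34. The global question is anchored to study start: "As compared to when you started the study, how would you rate your interstitial cystitis symptoms now".

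Section 4.2 adds a caveat: "it is recognized that there is no control group for this second phase (phase 2 and phase 2R) of the study", and the analysis is to be primarily descriptive. Section 2 lists both uses of these data among the trial's primary objectives: objective 4, "To obtain additional information on re-induction of intravesical BCG", and objective 5, the long-term response of patients who were responders at the end of Phase 1.

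**The concern.** IC symptoms and a patient's rating of them vary from visit to visit. A cut at week 34 sends some patients with an unusually bad visit into Phase 2 and some with an unusually good one into Phase 2R. Measured later, both groups move back towards their usual level even if nothing happens. When the later value is compared with the visit that made the cut, that movement is counted as change.

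For response status, the week-34 reference is 0% in Phase 2 and 100% in Phase 2R by construction, so each cohort can move only one way. In Phase 2 the movement would read as benefit of open-label BCG, and in Phase 2R as fading response. Those are the two questions behind objectives 4 and 5. A descriptive mean or percentage carries this bias as fully as a p-value does.

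**Working it through.** **Plan's own figure.** The protocol gives no number for Phase 2 or 2R. The nearest is the Phase 1 sample size in section 13.2, which reproduces: 103 per arm × 1.20 × 1.05 = 129.8, so 130 per arm and 260 in total.

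**Inputs.**
- Response rate p = 40%, the midpoint of the 30% and 50% in section 13.1; 30% and 50% are also shown.
- Correlation r between weeks 34 and 68: not given. Section 13.5 leaves within-participant variability to be assessed. Assumed 0.5 to 0.9.
- Correlation g between the global rating and a symptom score at the same visit: not given. Assumed 0.5 to 0.7.
- No true change after week 34, no effect of open-label BCG, and the same p at both visits.

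**Response status.** Let status at each visit be a standard normal score cut at c, where P(score > c) = p, and let B be the bivariate normal probability of response at both visits.
- Apparent conversion in Phase 2 = (p − B)/(1 − p)
- Apparent loss in Phase 2R = 1 − B/p

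| p | r | B | apparent conversion | apparent loss |
|---|---|---|---|---|
| 40% | 0.5 | 0.239 | 27% | 40% |
| 40% | 0.7 | 0.278 | 20% | 31% |
| 40% | 0.9 | 0.331 | 12% | 17% |
| 30% | 0.5 / 0.7 / 0.9 | 0.157 / 0.191 / 0.238 | 20 / 16 / 9% | 48 / 36 / 21% |
| 50% | 0.5 / 0.7 / 0.9 | 0.333 / 0.373 / 0.428 | 33 / 25 / 14% | 33 / 25 / 14% |

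The share of all patients moving each way is the same, p − B (12% at p = 40%, r = 0.7). The pooled rate does not move; only the split makes it look like change.

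**Symptom scores.** Drift from week 34 to week 68, in SD of the score:
- Phase 2, apparent improvement = g(1 − r)φ(c)/(1 − p)
- Phase 2R, apparent worsening = g(1 − r)φ(c)/p

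At p = 40%, c = 0.253 and φ(c) = 0.386, so the two multipliers are 0.644 and 0.966.
- Smallest (g = 0.5, r = 0.9): 0.5 × 0.1 × 0.644 = 0.03 SD and 0.5 × 0.1 × 0.966 = 0.05 SD.
- Largest (g = 0.7, r = 0.5): 0.7 × 0.5 × 0.644 = 0.23 SD and 0.7 × 0.5 × 0.966 = 0.34 SD.

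**Would an earlier reference visit help?** Let r_ref be the correlation of the chosen reference with week 34 (averaged over visits if a mean is used). The drift becomes proportional to r_ref − r, so the share of the bias that remains is (r_ref − r)/(1 − r).
- If all visit pairs are equally correlated, r_ref = r and nothing remains.
- If correlation decays with time, something does. Weeks 26, 18 and 68 lie 8, 16 and 34 weeks from week 34. Take a decaying part that shrinks by a factor d every 8 weeks on top of any constant part (the constant cancels). The share left is (d − d^4.25)/(1 − d^4.25) for week 26 and ((d + d²)/2 − d^4.25)/(1 − d^4.25) for the mean of weeks 18 and 26.
- d = 0.5 (d^4.25 = 0.053): 47% and 34%. d = 0.8 (d^4.25 = 0.387): 67% and 54%.

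Over a wider set of assumed decay patterns the share left was about 23-67% for week 26 and 18-54% for the mean of weeks 18 and 26. The mean reduced the bias in every pattern checked and removed it in none.

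**The case against.** The strongest defence is that section 4.2 already concedes the point: no control group, primarily descriptive, objectives that only seek information, and details of the final analysis deferred to a separate plan. Without a control, regression to the mean cannot be separated from effect in any case. This is right that the protocol makes no causal claim. But the caveat warns that change cannot be attributed; it does not warn that one reference was selected on, with a known and opposite direction in the two cohorts. Section 4.2 itself fixes the week-34 comparison, so this is not merely detail left for later.

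Four further objections stand and limit the point:
- Randomization is also a named reference, and the global question is anchored to study start. A reader might infer that week 34 is the only yardstick; it is not. Randomization is not wholly free of selection either, because entry required symptom thresholds: "This frequency criterion must be met at each of the two baseline-screening visits", with a similar rule for pain.
- A reader might go on to quote false-positive rates for a paired test of week 68 against week 34. Section 4.2 plans no such test. Such rates would also depend on how many patients enter: up to 15% may withdraw before week 34, and Phase 2 is voluntary.
- A reader might infer that replacing week 34 with week 26 gives an unbiased reference. That holds only if all visits are equally correlated.
- Starting Phase 2R at 100% is the ordinary definition of a durability cohort. The fault lies in reading all later loss as waning.

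Voluntary entry, open-label expectation and possible medication taper in Phase 2R act on the same contrasts and are separate matters.

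**Conclusion.** The point holds for the week-34 reference in Phase 2 and Phase 2R. Given a stable marginal response rate, the direction is certain for any correlation below 1: apparent improvement in Phase 2 and apparent loss in Phase 2R. The size is not fixed by the documents. At 40% response and assumed correlations of 0.5 to 0.9 it is 12-27% apparent conversion and 17-40% apparent loss, or about 0.03-0.23 SD and 0.05-0.34 SD on a symptom score. Real figures will differ, because response also depends on medication use and not every non-responder will enter Phase 2.

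A stronger reading, that the trial's main result is compromised, has no support: the randomized week-34 comparison uses neither the split nor week 68. The harm is to the interpretation of the descriptive follow-on phases. A cheap repair is worth making.

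**What to change.** In section 4.2:
1. Keep randomization and week 34 as references. Label week 34 as the selection visit, and state that change from week 34 to week 68 is not, on its own, to be read as a re-treatment effect or as loss of durability.
2. Show alongside them the mean of weeks 18 and 26 as a pre-selection Phase 1 reference: for the symptom indices and voiding diary in both phases, and for the SF-36 and MOS scale in Phase 2 only, since the Phase 2R schedule in Appendix B collects neither.
3. If the follow-up symptoms form carries the global question at weeks 18 and 26 (the protocol does not say), report the share of saline-arm patients not improved at week 18 or 26 but improved at week 34, as a rough benchmark for spontaneous conversion on the global item.

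The cost is wording and analysis only; Appendix B already schedules these forms at weeks 18 and 26. The limits should be stated with the results. The earlier reference reduces the bias but does not remove it when correlation decays with time, and it omits real change up to week 34. The saline benchmark spans 8 to 16 weeks rather than 34 and covers the global item, not the composite.
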